1.0 Research Design

1.1 Purpose/Specific Aims

To investigate the utility of using blood flow restriction (BFR) therapy in improving rotator cuff and proximal shoulder strength after surgical rotator cuff repair.

A. Objectives

This study aims to compare the improvements in range in motion and muscle strength between traditional therapy alone and BFR-augmented therapy during phase two of rehabilitation.

B. Hypotheses / Research Question(s)

Blood flow restriction in addition to outpatient physical therapy post-operative therapeutic exercise protocol will help to enhance muscle strength and endurance compared to post-operative therapeutic exercises alone.

1.2 Research Significance

Following surgical repair for rotator cuff tears physical therapy is necessary to decrease pain, improve range of motion (ROM), joint mobility, myofascial restrictions, and to regain functional strength in the respective extremity. As patient's progress from phase I into phase II or phase III, strengthening of the RTC and parascapular muscles to sustain ROM and regain function of the extremity.

Blood Flow Restriction (BFR) training has gained popularity in outpatient orthopedic physical therapy for a variety of musculoskeletal conditions¹. Pilot studies by Takarada et al. demonstrated that 50% limb occlusion with a tourniquet can induce muscle growth and increase limb strength.² Due to the use of light weight, high repetition training with partial occlusion of arterial inflow and venous return, patients have seen significant improvement in muscle hypertrophy and endurance. Many studies have looked at both proximal and distal improvements in hypertrophy, strength, and endurance with BFR on various musculoskeletal conditions. It has been previously demonstrated by Lambert et al. showed that BFR-augmented low intensity exercise increases lean shoulder and arm muscle mass, rotator cuff strength, and improved muscle endurance.³ However, the utility of BFR in the post-operative setting has not been well described for the upper extremity.

1.3 Research Design and Methods

A. Research Procedures

Potential subjects will be screened for possible inclusion in the study at the time of their evaluation by the surgeon during their clinic visit. Once they are seen for physical therapy, the physical therapist will review the study with the subject, answer any questions and consent patients who volunteer to participate in the study. Participants will be randomized to one of two groups. The control group receives standard post-operative physical therapy for rotator cuff repair and the experimental group receives the same standard therapy along with BFR therapy. BFR therapy entails the use of a tourniquet (blood pressure) cuff inflated to 50% of blood pressure occlusion, on the affected arm just distal to the affected shoulder, and then completing 4 sets of exercise with 30 seconds of rest in between. Use of BFR will occur along with physical therapy twice/week. Demographic data will be collected pre-operatively. Functional outcomes and PROMs will be collected 6 weeks into physical therapy, and repeated at 14 weeks into physical therapy.

B. Data Points

Range of motion, muscle strength, and muscle endurance is to be measured by approved physical therapists.

C. Study Duration

The study is expected to collect and analyze data for 2 years.

D. Endpoints

- Primary endpoints:
 - Isometric muscle strength
 - Muscle endurance
 - Shoulder Range of Motion
- Secondary endpoints:
 - Quick Disability of the Arms, Shoulder, and Hand (qDASH) score

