1.9 Data Collection

A. Primary Data Collection

- **Location:** Data will be collected during physical therapy visits at the UOA research sites.(Somerset, Wall, Morganville and Avenel). The data entry form that is completed after enrollment will be done in the clinic where the subject was consented. Data collection forms on REDCap will be completed during the physical therapy sessions by study members.
- **Process of Data Collection:**
Data will be collected by the specified team members. After enrollment to the study, the consenting team member will complete a data entry form that will record identifiers (name, email, phone number, race, gender and date of birth), gender, and date of surgery per the primary surgeon. After completing the specified physical therapy protocol per the study arm that the subject is assigned to, they will have range of motion (ROM) measured by a goniometer, muscle strength measured by a microFET 2 dynamometer, and muscle endurance measured by time to fatigue during exercise. qDASH questionnaires will be sent out to the subject and recorded to REDCap. All data collection will be done directly on REDCap.
- **Timing and Frequency:** Total duration of participation in this study will take 14 weeks. At the time of enrollment, demographic data will be collected. 6 weeks into post-operative physical therapy, functional outcomes (ROM, muscle strength, muscle endurance) and qDASH will be measured. At 14 weeks these same measures are repeated.
- **Procedures for Audio/Visual Recording:** N/A
- **Study Instruments:**
 - microFET 2 dynamometer
 - FDA Class II device
 - A handheld device that is used to measure muscle strength
 - The flat sensor is place of the muscle group to be tested, and then the subject flexes against the resistance of the device held against their limb
 - Device will record force in kilograms or pounds
 - Goniometer
 - FDA class I
 - A protractor designed to take measure joint angles
 - qDASH questionnaire
 - a validated questionnaire designed to assess how disability to the upper extremity affects quality of life.⁴
 - Intake Form
 - Form to be completed after enrollment to study
 - Will record subject identifiers (listed below), date of surgery, and gender
- **Ethnographic Studies, Interviews, Or Observation:** N/A
- **Subject Identifiers:**
 - name
 - Email
 - Phone number
 - Date of birth
 - Race
 - Gender

B. Secondary Data Collection

- **Type of Records:** N/A
- **Location:** N/A
- **Inclusion/Exclusion:** N/A

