2.2 Research Staff Training

All study team members have been CITI certified and physical therapists have completed formal training on blood flow restriction.

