4.4 Consent Procedures

A. Consent Process

▪ Location of Consent Process

Consent will be obtained at the follow sites:

- UOA Somerset
- Morganville
- UOA Wall
- UOA Avenel

The consent process will be done privately in-person with the subject in patient rooms at each study site.

▪ Ongoing Consent

While obtaining consent, patients will be reminded that they may contact any of the investigators with questions or concerns

▪ Individual Roles for Researchers Involved in Consent

The physical therapists will be responsible for obtaining consent for potential subjects. They will be notified by the attending surgeons who will screen patients regarding potential subjects for the study. At this time eligibility will be determined per the inclusion and exclusion criteria. Study team members will explain the purpose of the study, why the potential subject is being chosen for screening, what kind of time commitment and study activities the subject would be asked to participate in, potential risks and benefits associated with participating in the study, and what their alternative options are to joining the study.

- **Consent Discussion Duration**

15 minutes

- **Coercion or Undue Influence**

The primary surgeon caring the subject will not be a part of the consenting process to avoid undue pressure to join the study. Physical therapists will discuss the study with potential subjects and inform them that their alternative to joining the study is to decline participation which not affect their care.

- **Subject Understanding**

To ensure adequate understanding of the study, patients will be encouraged to ask questions about aspects they do not understand and the person obtaining consent will employ teach back methods to ensure patient understanding. They will have up to one day to decide whether they wish to join the study.

- **Protecting Privacy**

The consent discussion will occur in a private room with only the patient and the consenting individual present.

B. Waiver or Alteration of Consent Process

- **Waiver or Alteration Details:** N/A
- **Destruction of Identifiers:** N/A
- **Use of Deception/Concealment:** N/A
 - a. **Minimal Risk Justification:** N/A
 - b. **Alternatives:** N/A
 - c. **Subject Debriefing:** N/A

C. Documentation of Consent

- **Documenting Consent**

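### The primary endpoints are measured by physical therapists, the staff group trained to deliver BFR, and no masked or non-treating assessor is specified

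*Protocol*

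**What the plan says.** Section 1.3 B assigns the measurement of all three primary endpoints to one profession: "Range of motion, muscle strength, and muscle endurance is to be measured by approved physical therapists". Those endpoints, listed in section 1.3 D, are isometric strength, endurance and shoulder range of motion. The qDASH is the secondary endpoint.

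The same profession is tied to the intervention. Section 1.3 A says "Use of BFR will occur along with physical therapy twice/week", and section 2.2 says "physical therapists have completed formal training on blood flow restriction". Section 4.4 also gives physical therapists the task of obtaining consent.

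Section 1.9 A places data collection at physical therapy visits and adds: "Data collection forms on REDCap will be completed during the physical therapy sessions by study members". The methods are "muscle strength measured by a microFET 2 dynamometer, and muscle endurance measured by time to fatigue during exercise", with range of motion read by goniometer. For the dynamometer, the instrument description says that "the subject flexes against the resistance of the device held against their limb". The qDASH is sent to the patient and captured in REDCap.

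Neither section 1.3 nor section 1.9, the two that define what is measured, how and by whom, mentions masking of the assessor or an assessor who does not treat the patient.

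**The concern.** Patients cannot be masked to wearing a tourniquet cuff, and neither can the therapist who applies it. The remaining protection against expectation bias is an assessor who does not know the arm. The plan names who assesses but adds no such safeguard.

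The endpoints are of the kind that expectation can move. A reading from a device held by the tester depends partly on how firmly it is held and on the effort the patient is encouraged to make. Time to fatigue depends on effort, and the protocol states neither the criterion for ending the test nor who ends it. Goniometry requires the tester to judge alignment. The expectation also has a direction: section 1.1 B states the hypothesis that adding BFR improves strength and endurance, and section 1.2 cites earlier gains.

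Who measures and what they know is trial conduct. It must be settled before the first week-6 visit, and no later analysis can repair it. If arm-aware therapists do measure their own patients, a favourable result on a primary endpoint would be hard to separate from a tester effect.

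**Working it through.** **Step 1: what the text fixes.** Set side by side:

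- Assessor of all primary endpoints: approved physical therapists (section 1.3 B).
- Staff trained in BFR: physical therapists (section 2.2).
- When BFR is given: together with physical therapy (section 1.3 A).
- When and where data are recorded: at therapy visits, by study members (section 1.9 A).
- Masked or non-treating assessor: none specified in sections 1.3 or 1.9.

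The staff group that may measure is thus the group that is trained to deliver BFR, and nothing separates the two roles for a given patient. The treating therapist is permitted to measure, but not required to.

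**Step 2: which instrument applies to which endpoint.** The hand-held device serves strength only. Range of motion uses a goniometer, and endurance uses time to fatigue. Each has its own route for tester or effort influence.

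**Step 3: scale, for illustration only.** The protocol has no figure to reproduce here. It gives a total of 26 patients (sections 1.5 and 4.3) but no allocation ratio, alpha, power, effect size or SD. Assumptions: 1:1 allocation, so 26/2 = 13 per arm; two-sided alpha 0.05; a two-sample t-test with 13 + 13 − 2 = 24 degrees of freedom; no true effect; and a bias of *b* SD towards BFR in the quantity compared between arms.

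The standard error of the difference is SD × √(2/13) = 0.392 SD. The noncentrality is *b* × √(13/2) = 2.550 × *b*. The rejection rate is the probability that a noncentral t variable with 24 degrees of freedom falls outside the two-sided 5% limits.

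| Assumed bias (SD) | Noncentrality | Rejection rate per endpoint | Of which favouring BFR |
|---|---|---|---|
| 0 | 0 | 5.0% | 2.5% |
| 0.1 | 0.255 | 5.7% | 4.3% |
| 0.2 | 0.510 | 7.8% | 7.1% |
| 0.3 | 0.765 | 11.4% | 11.0% |
| 0.5 | 1.275 | 23.2% | 23.1% |

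The estimated difference is shifted by the full *b* SD at any sample size.

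**The case against.** The strongest reply is that several things a reader might infer are not stated.

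- **That the treating therapist measures their own patient.** Section 1.3 B speaks of approved therapists, and section 1.9 A of specified team members. Neither says who assesses whom, and an approved therapist could be someone other than the one treating. This stands: what the text supports is that the plan permits it.
- **That assessment is declared open.** The protocol is silent on masking; it does not reject it. Parts of the document, including section 2.1, are not in the text at hand. This also stands. However, the sections that define measurement are available and contain no safeguard.
- **That every primary endpoint uses the tester-held device.** Only strength does.
- **That measurement takes place in the middle of treatment.** Section 1.9 A has the forms completed during therapy sessions, but places the measurements after the arm's therapy protocol has been completed.
- **That the size of the bias is known.** The values of 0.2 to 0.5 SD have no source in the document. The calculation uses a two-sample t-test, whereas section 6.1 names paired t-testing and a Wilcoxon rank-sum test. The table shows what a given bias would do, not that it exists.
- **That therapists' role in consent adds to measurement bias.** It shows how far one staff group runs the trial, but has no direct bearing on the readings.

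It may also be said that the quoted sentence contains no error. That does not answer the point: assessor masking belongs in a protocol, and this protocol fixes the assessor while leaving the safeguard out.

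**Conclusion.** The point holds in a limited form. All three primary endpoints depend on the tester or on effort. They are assigned to the profession trained to deliver BFR and collected at therapy visits, with no assessor masking or non-treating assessor specified in the text at hand. The plan therefore allows an arm-aware, treating therapist to measure their own patient.

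The document cannot give the size of any resulting bias. Under the assumptions in the working, a bias of 0.2, 0.3 or 0.5 SD would raise false rejection per endpoint from 5% to about 8%, 11% or 23%, almost all of it in favour of BFR. It does not follow that bias will occur, or that a positive result would necessarily be a tester effect.

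The qDASH is a separate matter. Patients report it and know whether they wore a cuff. That limit comes with the intervention, and assessor masking cannot remove it.

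This should be changed before week-6 measurements begin, but it does not prevent the trial from running. If masked assessment is already intended, one sentence in the protocol settles the point.

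**What to change.** Amend sections 1.3 B and 1.9 A as follows:

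1. Wherever a site already has more than one approved therapist, the week-6 and week-14 measurements are taken by an approved therapist who has not treated that patient and is not told the arm. The cuff is off at measurement, and the patient is asked not to disclose the arm. The same assessor is used at both visits where possible.
2. Add two fields to the REDCap form: assessor ID, and aware of allocation (yes/no).
3. Report unmasked measurements as a limitation, with a descriptive sensitivity analysis if numbers allow. With 26 patients over four sites, about 26/4 = 6.5 each if evenly spread, such an analysis may not be informative.
4. Acknowledge that the qDASH remains patient-reported and unblinded.

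The cost is scheduling among existing therapists for two visits per patient, or 2 × 26 = 52 visits if all patients complete. The number of approved therapists per site is not shown, so the rule should apply only where a second one is already there, and no extra staff should be required. Sample size, endpoints and treatment are unchanged.

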1.4 Preliminary Data

We have not conducted a pilot study and there are no preliminary observational studies looking at this patient population.

1.5 Sample Size Justification

Sample size estimation via a priori conducted by Rutgers RUBIS determined that at least 26 patients should be enrolled in this study..

1.6 Study Variables

A. Independent Variables, Interventions, or Predictor Variables

The independent variables of this study are the use of traditional physical therapy and the use of traditional therapy with BFR therapy.

B. Dependent Variables or Outcome Measures

Outcome measures recorded for this study include: muscle strength, muscle endurance, shoulder range of motion, and qDASH score.

1.7 Drugs/Devices/Biologics

A. Schedule and Administration

N/A

B. Drug/Device Accountability and Storage Methods

N/A

0

1.8 Specimen Collection

A. Primary Specimen Collection

Types of Specimens: N/A

- Annotation: N/A
- Transport: N/A
- Processing: N/A
- Storage: N/A
- Disposition: N/A

B. Secondary Specimen Collection

N/A

Types of Specimens: N/A

Annotation: N/A

Transport: N/A

Storage: N/A

Disposition: N/A

1.9 Data Collection

A. Primary Data Collection

- **Location:** Data will be collected during physical therapy visits at the UOA research sites.(Somerset, Wall, Morganville and Avenel). The data entry form that is completed after enrollment will be done in the clinic where the subject was consented. Data collection forms on REDCap will be completed during the physical therapy sessions by study members.
- **Process of Data Collection:**
Data will be collected by the specified team members. After enrollment to the study, the consenting team member will complete a data entry form that will record identifiers (name, email, phone number, race, gender and date of birth), gender, and date of surgery per the primary surgeon. After completing the specified physical therapy protocol per the study arm that the subject is assigned to, they will have range of motion (ROM) measured by a goniometer, muscle strength measured by a microFET 2 dynamometer, and muscle endurance measured by time to fatigue during exercise. qDASH questionnaires will be sent out to the subject and recorded to REDCap. All data collection will be done directly on REDCap.
- **Timing and Frequency:** Total duration of participation in this study will take 14 weeks. At the time of enrollment, demographic data will be collected. 6 weeks into post-operative physical therapy, functional outcomes (ROM, muscle strength, muscle endurance) and qDASH will be measured. At 14 weeks these same measures are repeated.
- **Procedures for Audio/Visual Recording:** N/A
- **Study Instruments:**
 - microFET 2 dynamometer
 - FDA Class II device
 - A handheld device that is used to measure muscle strength
 - The flat sensor is place of the muscle group to be tested, and then the subject flexes against the resistance of the device held against their limb
 - Device will record force in kilograms or pounds
 - Goniometer
 - FDA class I
 - A protractor designed to take measure joint angles
 - qDASH questionnaire
 - a validated questionnaire designed to assess how disability to the upper extremity affects quality of life.⁴
 - Intake Form
 - Form to be completed after enrollment to study
 - Will record subject identifiers (listed below), date of surgery, and gender
- **Ethnographic Studies, Interviews, Or Observation:** N/A
- **Subject Identifiers:**
 - name
 - Email
 - Phone number
 - Date of birth
 - Race
 - Gender

B. Secondary Data Collection

- **Type of Records:** N/A
- **Location:** N/A
- **Inclusion/Exclusion:** N/A

- **Data Abstraction Form(s):** N/A

1.10 Timetable/Schedule of Events

	Before Surgery	Surgery	Week 6 of PT	Week 14 of PT
Demographics	x			
Range of Motion (degrees)			x	x
Muscle Strength (kg)			x	x
Muscle Endurance			x	x
qDASH score			x	x

2.2 Research Staff Training

All study team members have been CITI certified and physical therapists have completed formal training on blood flow restriction.

2.3 Other Resources

All therapy equipment and space will be provided by UOA. Computers for data recording will be provided by UOA.

3.0 Multi-Center Research

IAA and form 811, 830, and 1812a to be uploaded for research sites.

4.0 Subject Considerations

4.1 Subject Selection and Enrollment Considerations

A. Method to Identify Potential Subjects

Potential subjects will be identified by their attending surgeon.

B. Recruitment Details

One of the physical therapists will meet with them after being notified by the surgeon of a potential subject. They will explain the purpose of the study, what the study procedures entail, what the benefits and risks of the study, the implication of choosing or denying enrollment to the study, and what costs may be incurred if any by the subject. They will be given alternatives to not enrolling the study. The written consent form will be explained to them. They will have up to one day to consider enrolling into the study.

C. Subject Screening

Team members who are consenting the subject will assess their eligibility for enrollment to the study. This will be done through talking to the subject and asking them in person about the inclusion and exclusion criteria.

- **Inclusion Criteria**
 - 18 years of age or older
 - Has a small to medium sized rotator cuff tear requiring surgery
- **Exclusion Criteria**
 - Non-English speaker
 - History of prior shoulder surgery
 - History of complex regional pain syndrome after surgery
 - History of unstable hypertension, cardiopulmonary disease, vascular disease, deep vein thrombosis

D. Privacy Protections

All data entry and collection forms will be destroyed by way of shredding once the study personnel transcribe the data onto Rutgers REDCap. Access to the REDCap is password-protected and limited to study members only. Subjects will be assigned a numerical code assigned to them by REDCap. The data entry form will have identifiers such as name, email and phone number which are needed for REDCap to send out qDASH surveys and record responses. These identifiers are never linked to the name of the subject. Signed consent forms will be kept in a locked cabinet at each study site.

4.2 Obtaining Identifiable Information About Non-Subjects

N/A

4.3 Number of Subjects

A. Total Number of Subjects

We plan to enroll 26 subjects based on previous studies that also evaluated BFR. A priori power analysis with RUBIES will be conducted for a more concise target recruitment number.

B. Total Number of Subjects If Multicenter Study

26 subjects across all study sites.

C. Feasibility

This study protocol is feasible to execute given the prevalence of rotator cuff repairs that are surgically treated and the ease to which the data points can be collected.

4.4 Consent Procedures

A. Consent Process

▪ Location of Consent Process

Consent will be obtained at the follow sites:

- UOA Somerset
- Morganville
- UOA Wall
- UOA Avenel

The consent process will be done privately in-person with the subject in patient rooms at each study site.

▪ Ongoing Consent

While obtaining consent, patients will be reminded that they may contact any of the investigators with questions or concerns

▪ Individual Roles for Researchers Involved in Consent

The physical therapists will be responsible for obtaining consent for potential subjects. They will be notified by the attending surgeons who will screen patients regarding potential subjects for the study. At this time eligibility will be determined per the inclusion and exclusion criteria. Study team members will explain the purpose of the study, why the potential subject is being chosen for screening, what kind of time commitment and study activities the subject would be asked to participate in, potential risks and benefits associated with participating in the study, and what their alternative options are to joining the study.

- **Consent Discussion Duration**

15 minutes

- **Coercion or Undue Influence**

The primary surgeon caring the subject will not be a part of the consenting process to avoid undue pressure to join the study. Physical therapists will discuss the study with potential subjects and inform them that their alternative to joining the study is to decline participation which not affect their care.

- **Subject Understanding**

To ensure adequate understanding of the study, patients will be encouraged to ask questions about aspects they do not understand and the person obtaining consent will employ teach back methods to ensure patient understanding. They will have up to one day to decide whether they wish to join the study.

- **Protecting Privacy**

The consent discussion will occur in a private room with only the patient and the consenting individual present.

B. Waiver or Alteration of Consent Process

- **Waiver or Alteration Details:** N/A
- **Destruction of Identifiers:** N/A
- **Use of Deception/Concealment:** N/A
 - a. **Minimal Risk Justification:** N/A
 - b. **Alternatives:** N/A
 - c. **Subject Debriefing:** N/A

C. Documentation of Consent

- **Documenting Consent**

The consenting person will document consent in ordinance with the IRB requirements as stated in the Toolkit form. The patient will sign the consent form which will then be included in the visit note for the patient. A copy of the signed consent form will be provided to the patient, and it will be scanned into their medical record.

- **Waiver of Documentation of Consent (i.e., will not obtain subject's signature)**
N/A

